
Specific Aim 2. Evaluate the effectiveness of KanSurvive-ECHO for enhancing evidence-based survivorship care for rural breast, colorectal, lung, and prostate cancer survivors. Hypothesis: Compared to delayed intervention control, rural primary care practices randomized to KanSurvive-ECHO will demonstrate greater concordance with evidence-based survivorship care guidelines as measured by a composition score determined by change in EHR documentation consistent with guideline concordant care.

Specific Aim 3: Utilizing the Integrated Promoting Action on Research Implementation in Health Services (i-PARIHS) framework (6) describe key facilitators and barriers to implementation of KanSurvive-ECHO including innovation, recipients, context, and facilitation. This novel project will provide a model for development of a community of practice using practice facilitation and Project ECHO to improve the management and follow-up of cancer survivors in the acute and extended phases of cancer survivorship.

B. Background and Significance

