
Approach: Research Design will include observational research plus pilot testing of the KanSurvive-ECHO intervention

Conceptual Framework: Informed by the Integrated Promoting Action on Research Implementation in Health Services (i-PARIHS) implementation framework, the KanSurvive intervention will target EBP improvement in rural primary care. Our recent pilot work using an updated 4-session case-based curriculum relied on utilization of practice facilitators providing on-site training to rural primary care teams. This project will expand to move beyond traditional training models, to a hands-on practice re-organization. Additional formative data collection with site visits and practice observation will inform final refinement of the KanSurvive ECHO Intervention. The delayed intervention control and KanSurvive-ECHO practices will be compared on outcomes specified by the RE-AIM evaluation framework (e.g., Reach, Effectiveness, Adoption, Implementation fidelity and acceptability, and Maintenance after 6 months).

Study Design: Using a Hybrid Type II study design, (51) the proposed study includes a three-aim plan for further assessing the rural practice environment and refining the KanSurvive-ECHO intervention (Aim 1), testing the effectiveness of KanSurvive-ECHO (Aim 2), and describing key facilitators and barriers to adoption of KanSurvive-ECHO intervention components in rural primary care (Aim 3). We will recruit 20 rural (defined using RUCA-UR codes) primary care practices from the KPEPPER network for a delayed intervention control trial.

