Intervention refinement: The research team will work to review Phase 1 data with participating practice leads and champions, Rural ACO leaders and transformation specialists, regional content experts, and the KPPEPR Board to come up with a set of 4-8 major recommendations for intervention. They will then review previously developed pilot KanSurvive materials and suggest refinements based on these major recommendations. The research team and staff will utilize these suggestions to refine and finalize the KanSurvive intervention for Phase 2 (See Figure 6, Suggested study schema).

4.6 Phase 2: Implementation of the cluster-randomized controlled trial, with delayed start control arm Figure 6: Suggested Study Schema

Practice Facilitation. Due to the complexity of translating evidence-based guidelines into practice, significant gaps continue to exist between research evidence and practice.(58, 59) Knowledge is rarely sufficient to support the adoption of EBP behavior,(60, 61) with didactic education or passive dissemination strategies largely ineffective. Practice facilitation has emerged as an effective practice change approach and will be a key implementation strategy in the proposed study. Taken literally, facilitation means “to make easier”. (56, 62)Practice facilitation is broadly defined as “a supportive service provided to a primary care practice by a trained individual or team of individuals. (63)These individuals use a range of organizational development, project management, quality improvement (QI), and practice improvement approaches and methods to build the internal capacity of a practice to help it engage in improvement activities over time and support it in reaching incremental and transformative improvement goals. This support may be provided onsite, virtually (through phone conferences and Webinars), or through a combination of onsite and virtual visits” (AHRQ, <https://pcmh.ahrq.gov/page/practice-facilitation>). Practice facilitators, also known as practice coaches or quality improvement coaches, are specially trained individuals who help practices engage in implementing guidelines and developing capacity for continuous quality improvement. (18)

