2. *Effectiveness* will be measured as % change in electronic health record evidence of guideline concordant care from pre- to 6-months post- KansSurvive-ECHO in intervention versus delayed intervention control practices. Using baseline EHR assessments in charts of cancer survivors identified from hospital registries we will compare the pre- and post- percentages of these survivors with best practice alerts, orders sets, health maintenance modules or other tools that note specific survivorship care services that they should be receiving to meet guidelines (Table 3) (67-74)

3. *Adoption* will be measured by calculating the representativeness of the participating rural primary care practices. Specifically, participating rural primary care practices will be measured on their size and their patient panels and will be compared as a group to the overall data that is available for all rural primary care practices in the state of Kansas on these key variables to assess for the representativeness of participating practices.

4. *Implementation Consistency: In addition to project feasibility and acceptability, we will assess facilitators and barriers to KansSurvive adoption using the i-PARIHS framework (Aim 3). Fidelity:* We will refine KansSurvive fidelity assessment consistent with Schoenwald et al.(55): (1) identifying relevant components for monitoring across practice facilitation and ECHO components (e.g., specificity, necessity, degree of precision), (2) determining who would provide the ratings, (3) obtaining the ratings, and (4) creating a summary score for the ratings. We will monitor fidelity to the KansSurvive components, with checklists associated with practice facilitation from multiple perspectives (e.g., participating practice teams, facilitators, ECHO subject matter experts). *Attendance and Participation.* Percent attendance will be

calculated for each rural primary care practice as the percent of practice facilitation and ECHO sessions attended divided by the total number of sessions offered. For both groups' participation the amount of between session work completed (as a percent).

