5. **Maintenance:** Our experienced team will conduct structured interviews with participating rural primary care practices to assess their ability to sustain key components of the KanSurvive ECHO program over time and maintain effects at 6-months, including policies and procedures to support the cancer survivorship guidelines. Identification of cancer survivors with breast, lung, colon and prostate cancer. In order to identify survivors under the care of a particular PCP, we will engage the local/affiliated hospital's tumor registry. A list of all primary care providers participating in the intervention will be compiled using several key fields: "following doctor" (primary care provider) and the type of cancer (breast, colon, lung, and prostate cancer). This PCP list will be given to local hospitals, which will run a report to identify all cancer survivors with breast, lung, colon and prostate cancer affiliated with the "following doctor". Additional variables from the tumor registry will include demographics, stage, treatment, treating oncologist. Each primary care provider participating in the intervention will receive their list of affiliated patients. (75)

Data extraction will be completed by an "honest broker" who will utilize a consistent algorithm across all EMR systems to record evidence of guideline concordant survivorship care through a HIPAA waiver to allow such data abstraction without consenting individual patients. Medical record extraction is considered the "gold standard" and will be the primary objective data source for this trial. Practice-level data gathered from participating practices will be recorded directly into a secure KUMC REDCap database which requires username and password verification. Only designated research staff will have access to research information. The data collection survey tool built in REDCap will be pilot tested internally and modified as needed to ensure clarity for the data collector.

Table 3: Measure change in EHR documentation Concordant with Evidence-based Cancer Screening by Diagnosis

Cancer Diagnosis	Breast	Lung	Colon	Prostate	EHR Documentation Baseline (Yes/No)	EHR Documentation Post (Yes/No)
Recommended screening based on diagnosis*	Mammogram (annual)	CT (annual)	Colonoscopy (frequency specified by risk)	PSA (annual or more frequent based on risk and time since diagnosis)		
Distress/Depression Screen (PHQ9) (annual)	X	X	X	X		
Lifestyle Recommendations	X	X	X	X		

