76. Centers for Disease Control. Cancer Registry Research Approval Process: Classification of States by Level of Approval Required2018.

ANALYSES

Quantitative Data:

- Differences in cancer survivorship performance indicators before and after intervention were assessed using Chi-square or Fisher Exact tests.
- Clinical characteristics are summarized with frequencies and percentages.
- Demographic and patient characteristics are summarized descriptively with respect to frequencies and percentages for categorical variables, and mean, standard deviation, median, minimum and maximum for continuous variables.
- Differences in surveillance rates by tumor types before and after intervention were assessed using Fisher Exact tests.
- Statistical tests were considered significant if $p < 0.05$.

Qualitative Data:

- Interview notes, transcripts of practice facilitation meetings, and field records were compiled and analyzed using the i-PARIHS framework to evaluate barriers and facilitators to implementation.
- A thematic network analysis was employed by first noting initial impressions.
- Transcripts were independently reviewed line-by-line and preliminary codes were applied to relevant passages.
- A coding framework was developed with clear code descriptions, organizing data into themes and sub-themes.
- This framework was systematically applied to all transcripts using Dedoose software to ensure consistent and meaningful codes across the dataset.

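### Aim 2 compares randomised arms, but the only tests listed are before/after tests that ignore arm and practice, and the outcome is described in two different ways

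*Combined protocol and SAP*

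**What the plan says.** The design and the aim are comparative. Specific Aim 2 expects practices randomised to KanSurvive-ECHO to show greater concordance than delayed-control practices, "as measured by a composition score determined by change in EHR documentation consistent with guideline concordant care". Section 4.6 is headed "Implementation of the cluster-randomized controlled trial, with delayed start control arm". The Conceptual Framework paragraph says: "The delayed intervention control and KanSurvive-ECHO practices will be compared on outcomes specified by the RE-AIM evaluation framework". The Effectiveness item of the RE-AIM evaluation measures percentage change "from pre- to 6-months post- KansSurvive-ECHO in intervention versus delayed intervention control practices".

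The ANALYSES section (Quantitative Data) lists two inferential comparisons: "Differences in cancer survivorship performance indicators before and after intervention were assessed using Chi-square or Fisher Exact tests" and "Differences in surveillance rates by tumor types before and after intervention were assessed using Fisher Exact tests". The significance threshold is 0.05. The rest of that list is descriptive summaries.

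On the outcome, the Effectiveness item describes the percentage of survivors whose charts carry alerts, order sets and similar tools, and refers to Table 3. Table 3 is titled "Measure change in EHR documentation Concordant with Evidence-based Cancer Screening by Diagnosis" and lists Yes/No items with one Baseline and one Post column.

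**The concern.** Practices are randomised to a delayed-start control so that changes happening anyway can be separated from the effect of the intervention. A before/after test does not make that separation. The protocol itself gives reason to expect change without facilitation: its Practice facilitation section cites a cluster-randomised trial whose control arm improved by 33%. If the listed tests were the evidence for Aim 2, a general rise in documentation could not be told apart from an effect of KanSurvive-ECHO.

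Two further gaps add to this. The named tests treat each chart as an independent observation, although practices are the randomised unit and the data are collected before and after in the same practices. And it is not clear which outcome the comparison would use.

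**Working it through.** The documents give no power, effect size or intracluster correlation (ICC), so there is no planned figure to reproduce.

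**1. Passages side by side**

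| Place | Contrast | Method |
|---|---|---|
| Specific Aim 2 | randomised arm vs delayed control | none |
| Conceptual Framework | arms compared on RE-AIM outcomes | none |
| 4.6 Phase 2 | cluster-randomised, delayed-start control | none |
| RE-AIM Effectiveness | change, intervention vs control | none |
| ANALYSES, Quantitative Data | before vs after, several indicators | chi-square or Fisher |
| ANALYSES, Quantitative Data | before vs after, by tumour type | Fisher |

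The contrast is stated without a method, and the methods are stated for a different contrast.

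**2. What each test responds to.** Let s be the change shared by both arms and e the intervention effect. A before/after test in intervention practices examines s + e. A between-arm comparison of change examines (s + e) − s = e. When e = 0 and s is not zero, only the first tends to reject.

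**3. Illustration with e = 0.** From the documents: 20 practices, and an average of 200 survivors per practice as a recruitment criterion. Assumed: 10 practices per arm, all 200 charts abstracted, baseline 50%, independent records, two-sided 0.05.

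SE = √{[p0(1 − p0) + p1(1 − p1)]/n}, z = (p1 − p0)/SE, rejection probability = Φ(z − 1.96) + Φ(−z − 1.96).

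For a 3-point rise and n = 10 × 200 = 2,000 per period: SE = √[(0.2500 + 0.2491)/2,000] = 0.0158, z = 1.90, probability = 0.48.

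| Charts per period | 2 points | 3 points | 5 points |
|---|---|---|---|
| 2,000 | 0.24 | 0.48 | 0.89 |
| 500 | 0.10 | 0.16 | 0.35 |
| 200 | 0.07 | 0.09 | 0.17 |

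A simulation with 2,000 charts per period allowed practices to differ in their change (SD 0 to 5 points), up to half the records to be shared between periods, and baselines of 50–60%. The before/after test rejected in 16–33%, 47–50% and 80–96% of trials for rises of 2, 3 and 5 points. With no rise at all it rejected in under 1% to about 16%. The spread therefore reflects ignored clustering and pairing as well as a shared trend. A practice-level between-arm ANCOVA rejected in 4.7–5.3% throughout, as expected by construction.

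**4. Adding arm to a chi-square test is not enough.** For a chart-level comparison between arms, the design effect is 1 + (200 − 1) × ICC. With an assumed ICC of 0.01 it is 2.99, and with 0.10 it is 20.9. The 2,000 charts in an arm then carry the information of about 669 (2,000/2.99) or 96 (2,000/20.9).

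**5. The scoring rule changes the effect.** Table 3 has six items not flagged exploratory. Suppose all six apply, are independent, and rise from 50% to 60%. A mean-of-items score rises by 10.0 points. An all-or-none score rises from 0.5^6 = 1.6% to 0.6^6 = 4.7%, or 3.1 points. The tool-based percentage in the Effectiveness item is a third quantity.

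**The case against.** The strongest reply is that this is a combined protocol and SAP, and the protocol part does plan the arm comparison. That is right. A reader might infer that the trial never intended to compare its arms; the Conceptual Framework and the Effectiveness item rule that out. What is missing is the method.

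A reader might also infer that the sponsor will claim effectiveness from before/after p-values. No passage says so. The risk comes from those being the only tests listed.

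The rejection rates are open to challenge too. The rises, SDs, baselines and chart numbers are assumed, and 200 is a practice volume, not a stated abstraction count. A 50–60% baseline fits poorly with the tool-based measure, since the recruitment section reports no EHR mechanisms for identifying survivors or guiding their care in any pilot practice. All of this stands, so the rates show a direction and are not this trial's error rates.

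It is tempting to say that the score is built from Table 3, or that control practices will have started before follow-up. Aim 2 does not tie the score to Table 3. The Study Timeline table is too broken in the available text to settle the second.

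Finally, the Approach section speaks of observational research plus pilot testing, and the ANALYSES section is in the past tense. If only a descriptive pilot was meant, the comparative hypothesis of Aim 2 would need to change. If the analyses are done, the mismatch remains and affects what may be claimed.

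**Conclusion.** The concern holds in this form: the listed inferential tests cannot answer Aim 2, because none compares arms, none respects practice as the randomised unit, and none is primary. The primary outcome is also described inconsistently between Specific Aim 2 and the RE-AIM Effectiveness item. The absent scoring rule on its own would be missing detail, and it is limited to the text available for review.

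The size cannot be fixed from the documents. Under the stated assumptions, the chance that a shared 3-point rise appears significant runs from about 9% with 200 charts per period to about 48% with 2,000. The main conclusion does not depend on these figures; it follows from the wording of the sections and from the algebra in step 2.

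**What to change.** In the ANALYSES section, make the primary Aim 2 analysis one between-arm comparison of the follow-up outcome, adjusted for baseline and accounting for practice. A practice-level ANCOVA with a t reference would do (17 df with 20 practices), as would a mixed model or GEE with a small-sample correction.

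Reconcile Specific Aim 2 and the Effectiveness item into one primary outcome with a stated scoring rule: which items enter, the denominator, how non-applicable and one-time items count, and how patients are aggregated to practice.

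For this comparison, use follow-up data from before control practices start the intervention, and reconcile the 6-month follow-up point with the Study Timeline. Table 3 plans only Baseline and Post, so dated EHR entries may be needed.

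Report before/after and tumour-specific tests as secondary or descriptive. If analyses are complete, label the re-analysis post hoc. Without a between-arm analysis, do not claim effectiveness versus control from before/after tests.

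The cost is SAP wording, a scoring decision, possibly entry dates in the extraction, and some analysis work. Precision will be limited. With 10 practices per arm and 17 df, the difference detectable at 80% power is about 2.97 × SD × √(2/10) = 1.33 × SD. That is 6.7, 10.6 or 13.3 points for an assumed residual practice SD of 5, 8 or 10 points.

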Understanding current practice and management of cancer survivors by primary care and oncology care teams. The Midwest Cancer Alliance (MCA), the outreach arm of The University of Kansas Cancer Center (KUCC), and Kansas Patients and Providers Engaged in Prevention Research (KPPEPR), completed semi-structured interviews and focus groups in rural primary care and oncology practices across Kansas in 2016-17. Qualitative methods were used to obtain in-depth information regarding providers' beliefs, current practices and barriers related to cancer survivorship care so that future interventions could be tailored to this population of providers in rural Kansas. Focus groups were audio-taped and transcripts were produced. Qualitative analysis was conducted by independent reviewers using an iterative process to reach consensus on primary themes and definitions. Thematic categories were identified and recorded. Transcripts were then reread by each team member to assure thematic fit for all focus group content. Triangulation and consensus were used throughout the analysis phase to maximize trustworthiness of findings. Primary care and oncology teams face similar cross-cutting barriers in caring for cancer survivors including: educational gaps; communication of history, treatment and recommendations; EHR integration; and lack of resources, highlighted in table 1. Based on the complex needs of cancer survivors and the complexity of health care delivery, an organized approach is needed to align survivorship care delivery across settings. (49)

Table 1: Cross-Cutting Themes

Cross-cutting Themes	Summary Statements from Primary Care Interviews	Participant Quotes from Primary Care Interviews
Organizational Structure	
 Broader healthcare issue Lack of EHR integration and systems within practice; causing communication issues. Difficulty finding and consolidating information from various sources; scanned documents are essential to have, if it is not on the problem list, it is not on the providers radar. Practices participating in ACOs are more equipped to support care coordination. 	
 "It's one thing to collect the data, it's another thing to input the data and then it's another thing to put the data in the right place where you can come back and retrieve it in a systematic format. So you have streams then that have the potential for breakdown or challenges." "...and then you have to have a system that can take that and make it very helpful, yes. But that requires the whole system to change, not just one part of it." "So a single EHR that everybody uses that was the same format...that would change medicine."
Provider and Patient Engagement & Communication	
 Broader healthcare issue PCPs want 1-2 pages with specific recommendations. PCPs see oncologists as the experts who should be provided with recommendations. PCPs mentioned the different approaches to treatment and management. Oncologists tend to continue treatment. PCPs are concerned about the negative effects of the treatment on the patient and patient's quality of life. No consensus on how much responsibility patients should have. Some wanted the patient to have more responsibility, but others felt like patients were not reliable. Rural: personal relationships, better communication with patients and specialists than in urban communities. 	
 "There's nothing more confusing to the patient than we tell them these years and the oncologist says seven, the internist says don't take it at all... so if we had a way to know what the oncologist was thinking..." "We have oncologists that are excellent...but we don't have a good coordinator to help me. We use doctors who either call us directly themselves or they have someone that contacts us. When they need help, they don't know who to call." "And then you get like 423 pages of notes that you have to try to sift through and figure out where everything is..." "We do know people are everywhere...we will go out to dinner with them when they are here...when I have a diagnosis of cancer, I will text them right away and say can you see them and they'll say yup...We do have those good relationships."
Access to Survivorship Care and Resources	Lack of survivorship resources in rural communities, particularly with mental health support.	
 "I don't know of any community that has good mental health, not in Kansas. We have probably the poorest mental health there is." "...but people can't go see a specialist because they can't afford to or they don't have the transportation means. We have very limited resources out here."
Knowledge Gaps	PCP teams shifted the conversation to acute cancer treatment issues (transportation, funders for treatment), rather than long-term survivorship issues.	
 "I always just assume that I'm letting the oncologist figure that stuff out, but I am not real well-educated on all those things I should be doing 5, 10, 15 years later. For sure, I think there's a gap in knowledge base for more physicians."

Map of Group

KanSurvive

1.1.a. Test the feasibility and acceptability of a survivorship care educational and practice facilitation intervention. The KanSurvive Pilot Intervention was undertaken to establish

feasibility and acceptability within our network. [name], [name], and team adapted materials (50) for a pilot project to use practice facilitation to deliver in-person content on EBP survivorship care guidelines for acute and extended cancer survivorship care in rural primary care (CDC15-1501). The team worked with rural primary care providers and oncologists to develop a series of patient case summaries for colon, breast, and prostate cancer, as well as for an adult survivor of childhood cancer. Patient cases were then merged with appropriate content for delivery during practice facilitation sessions. The curriculum was informed by findings from the focus groups conducted in 2016-2017 (49) and reviewed by Kansas cancer survivors and advisors (Patient and Investigator Voices Organizing Together or PIVOT) (Figure 2). Seven rural primary care practices (Figure 5) completed 4 hours (1 hour per session) of on-site practice facilitation + cancer survivorship training. Practice facilitation was delivered by an oncology nurse/navigator with >25 years of experience and community health Physician Assistant (PA). Sessions included skills for identifying survivors within the practice, where to find EBP guidelines, and reviewing common causes and management of acute and extended survivorship issues. Facilitation activities also provided access to additional local, regional, and national web resources (<http://kscancerpartnership.org>), though a collaboration with the Kansas Cancer Partnership and the Kansas Department of Health and Environment (CDC15-1501). Follow-up data collection has recently been completed and we identified that participating rural primary care practices reported high satisfaction with the approach and knowledge gains, but challenges in translating knowledge into practice. They reported benefiting from the onsite practice facilitation but the majority felt they would like additional facilitation and other support over a longer period of time due to the complexity of the practice change needed to implement cancer survivorship guidelines across breast, colorectal, lung, and prostate cancer. Participants liked "real life" examples from the facilitators. They were interested in talking with other rural practices about how they worked through challenges in putting EBP guidelines into practice in very busy, often low-resource settings. Participants asked for consultation and ways to increase communication with survivorship experts in order to support specific patients in their practices. Finally, practices had needs for quality improvement strategies with limited trained staff and strategies to extract and utilize their own cancer survivor data. Since most practices reported rarely seeing "survivorship care plans" (or post treatment plans from oncologists), they were interested in easy tools and resources for moving their care processes in line with survivorship guidelines. Throughout the pilot intervention and focus groups, the need for role delineation and improved communication between primary care and cancer care teams was evident.

Approach: Research Design will include observational research plus pilot testing of the KanSurvive-ECHO intervention

Conceptual Framework: Informed by the Integrated Promoting Action on Research Implementation in Health Services (i-PARIHS) implementation framework, the KanSurvive intervention will target EBP improvement in rural primary care. Our recent pilot work using an updated 4-session case-based curriculum relied on utilization of practice facilitators providing on-site training to rural primary care teams. This project will expand to move beyond traditional training models, to a hands-on practice re-organization. Additional formative data collection with site visits and practice observation will inform final refinement of the KanSurvive ECHO Intervention. The delayed intervention control and KanSurvive-ECHO practices will be compared on outcomes specified by the RE-AIM evaluation framework (e.g., Reach, Effectiveness, Adoption, Implementation fidelity and acceptability, and Maintenance after 6 months).

Study Design: Using a Hybrid Type II study design, (51) the proposed study includes a three-aim plan for further assessing the rural practice environment and refining the KanSurvive-ECHO intervention (Aim 1), testing the effectiveness of KanSurvive-ECHO (Aim 2), and describing key facilitators and barriers to adoption of KanSurvive-ECHO intervention components in rural primary care (Aim 3). We will recruit 20 rural (defined using RUCA-UR codes) primary care practices from the KPEPPER network for a delayed intervention control trial.

Target population: The project will recruit rural-dwelling cancer survivors and KPEPPER primary care practices that care for these patients. The 2016 estimates for The University of Kansas Cancer Center (KUCC) catchment area, were for 22,000 people with a cancer diagnosis, and more than 8,500 cancer deaths. (52) The catchment area, includes 123 counties in Kansas and western Missouri (78%) are either classified as rural or frontier counties, with a total population of 4.4 million. Utilizing the 2010 Rural Urban Commuting Areas (RUCA) the data demonstrates that the KUCC catchment area includes a high percentage of individuals residing in rural communities with RUCA categories 4-10. The rural counties (RUCC 4-9) in our project area have a range of percent individuals in poverty from 7.5 to 22.3% and has a slightly higher percentage of those without health insurance at 11.74%. (53, 54) The poverty threshold in 2017 for a household with one adult under 65 years of age was \$12,752 and for two adults with two children was \$24,782. (53)

Recruitment of sites

Rural Primary Care Clinics: We have experience recruiting rural primary care clinics across all of rural Kansas. The Kansas Patients and Providers Engaged in Prevention Research (KPPEPR) network is a practice-based research network that has served as host to four previous NIH R01-funded trials. The Board of the network has unanimously agreed to support this project, (see letter of support). They have advised us that they believe we will have no difficulty recruiting the twenty practices needed for this study. We will identify clinics that care for an average of 200 patients that are survivors of breast, colon, lung or prostate cancer. This volume will allow participating practices to observe meaningful changes in patient survivorship care implementation and outcomes. From our pilot work, primary care providers described sending almost all (~95%) of their newly diagnosed cancer patients to the same, local oncology providers/practices. Currently, no EHR-based mechanisms are in place in any of the pilot practices we have worked with to systematically identify cancer survivors or to guide survivorship care through best practice alerts, orders sets, health maintenance modules or other tools. However, an improved understanding of the capacity of the participating primary care clinics will be informed by a recently awarded rural supplement to the KUCC cancer center P30 ([name] & [name], co-leads). Data from all participating clinics will be extracted from EHRs by an "honest broker" who will utilize a consistent algorithm across all EMR systems to record evidence of guideline concordant survivorship care. We anticipate receiving a HIPAA waiver to allow such data abstraction without consenting individual patients.

Planning and engagement

Phase 1 In order to address the cross-cutting implementation barriers in caring for cancer survivors identified in the pilot, (55) we propose to formally describe care gaps, infrastructure needs and processes of care for acute and chronic cancer survivorship in rural primary care focusing on breast, colorectal, lung, and prostate cancer survivors and utilize this formative information to further refine the KanSurvive intervention, including the practice facilitation and Project ECHO approaches.

The Integrated Promoting Action on Research Implementation in Health Services (i-PARIHS) framework will guide (Harvey & Kitson, (14) the discovery of capacity for implementing the EBP for cancer survivors and further refining the KanSurvive practice facilitation strategies. i-PARIHS posits that core components of successful implementation are innovation, recipients (individual and collective), context (inner and outer), and facilitation. Successful implementation takes place when facilitation (i.e., KanSurvive) promotes the acceptance and use of an innovation (i.e., EBPs) based on recipients' needs (i.e., primary care and cancer care teams see improving survivorship care as important) and on the nature of the implementation context (i.e., unique external and internal features of rural primary care). We will also use concepts from this framework to identify facilitators/barriers to implementation of KanSurvive ECHO (Aim 3). Definitions and associated evaluation questions will be drawn from the i-PARIHS developers (14, 16) as well as informed by the PARIHS implementation guide (Table 2). (17)

Table 2 I-PARIHS DOMAINS TO INFORM PRE-TRIAL (Aim 1) and POST-TRIAL (Aim 3) EVALUATION			
i-PARIHS Domain	i-PARIHS Subdomains	Informant(s)	Measurement
Innovation	Underlying knowledge sources Clarity Degree of fit with existing practice and values (compatibility or contestability) Usability Relative advantage Trialability Observable results	Rural primary care and oncology practices: leadership and team members	A mixed methods approach will be used across domains including: Semi-structured Interviews informed by Harvey & Kitson (56) as well as related implementation domains from the CFIR interview guide and consistent with Stettler et al.(17)
Recipients	Motivation Values and beliefs Goals Skills and knowledge Time, resources, support Local opinion leaders Collaboration and teamwork Existing networks Power and authority Presence of boundaries	Rural ACO leaders and transformation specialists Subject Matter Experts	Practice environment checklist Organizational Change

Context	Local level: Formal and informal leadership support Culture Past experience of innovation and change Mechanisms for embedding change Evaluation and feedback processes Learning environment Organizational level: Organizational priorities		Manager(57)
	Senior leadership and management support Culture Structure and systems History of innovation and change Absorptive capacity Learning networks External health system level: Policy drivers and priorities Incentives and mandates Regulatory frameworks Environmental (in)stability Inter-organizational networks and relationships		
Facilitation	On-Site ECHO Telehealth	Purpose, external and/or internal role Expectations and activities Skills and attributes of facilitators	Facilitators Rural primary care and oncology practices ECHO expert panels Practice Environment Checklist Facilitator logs Acceptability, Feasibility, & Fidelity ratings

With enrolled study sites will complete an assessment of baseline organizational characteristics informed by the i-PARIHS framework. Semi-structured interviews will be completed with clinical and administrative key informants to further assist in identifying potential barriers and facilitators to implementing cancer survivorship guidelines and the KanSurvive intervention, focused on organizational processes and workflow. Based on the revised questions from the pilot, practice teams will complete interviews to inform the I-PARIHS domains (innovation, recipients, and context). This information will in turn inform KanSurvive content and implementation strategy modification. Organizational readiness to change will be assessed using the interview guides and the Organizational Change Manager survey, a validated readiness tool. (57)

Data collection:

1.) Key informant interviews. We will conduct key informant interviews with the following: a) Rural primary care practice providers, managers, nursing and staff members; b) Rural Oncology practice providers, managers, nursing and staff members; c) Rural Accountable Care organization leaders and practice transformation specialists (also involved in P30 Rural Supplement); d) Subject matter experts including the ECHO expert panelists; and e) Rural cancer survivors. We will use a semi-structured interview guide organized by i-PARIHS constructs. This includes gaining input on workflow mapping, processes of care and any ongoing quality improvement efforts. Drs. [name] and [name] will recruit key informants and conduct interviews alongside the project manager. 2.) Baseline study site assessment. Using direct observation and on-site data collection the project manager will gather data on practice-level variables that impact the implementation of EBP, including number of FTE staff, turnover rates, clinic volume, policies and systems, and technology use (EHR and telehealth). We will develop and use a practice environment checklist to inventory current policies, workflows, and staff roles and responsibilities in relation to cancer survivorship. Fieldnotes and schematics will be recorded and kept for team analysis. Practice personnel will also complete the Organizational Change Manager (Gustafson et al., 2003), a validated 60-item readiness measure with 15 domains that complement many i-PARIHS subdomains.

Data analysis:

1.) Key informant interview analysis. Key informant interviews will be audio-taped and transcribed. Qualitative analysis will be conducted by independent reviewers using an iterative process to reach consensus on primary themes and definitions. Thematic categories will be identified and recorded. Transcripts will then be reread by each team member to assure thematic fit for all key informant content. Triangulation and consensus will be used throughout the analysis phase to maximize trustworthiness of findings. 2.) The baseline study site assessment information will be tabulated and summarized per practice, including general descriptive information on staff, patient volumes, policies and technology use. Workflows and schematics will be mapped. Site summary data will be merged with organizational readiness measures to characterize practices in relation to peers.

